### Enrollment and Consent

Prospective participants, men and women with MS, will be recruited from the MS Clinic in the Dept. of Neurology at UIOWA ([name]), through advertisements on UIOWA Campus, and through mass email. For those recruited at the clinic, [name] will discuss the study with potential participants and provide them with a copy of the informed consent and/or consent summary (if requested) and a copy of the recruitment flyer to contact the other study personnel. All other experimental procedures will be performed in the INPL (Director: [name], FACSM). Interested individuals from any recruitment source (i.e., clinic, flyers, website, email) will contact study personnel and perform an initial phone screening via a

questionnaire. Contact information for the prospective participant will be accessible only to the research staff according to HIPPA regulations. After completion of the phone questionnaire, INPL personnel will schedule the participant's first visit (10 total).

During the first visit, subjects will review the consent summary and consent form before signing the consent document. The PI or research staff will answer all questions asked by the potential subject and the subject will be informed of all potential risks before signing the consent document. Subjects will in no way be coerced to sign the consent form and will be informed that it is their choice whether to volunteer for this study. Even after subjects sign the consent, they are free to withdraw from the study at any time and for any reason.

### Risks for subjects

Physical well-being: Potential risk include muscle cramps/spasms during strength testing.

tDCS safety: tDCS is a non-invasive brain stimulation technique in which a very weak electrical current is applied to the scalp. tDCS has been conducted on humans and animals for many years and no evidence has emerged to suggest that it is harmful or has ever induced a serious side effect. However, the safety of tDCS is dependent on current strength, electrode size, and stimulation duration. Accordingly, these parameters have been investigated to establish safe and effective stimulation parameters for tDCS applications in research involving human subjects. However, recently experts in tDCS research have indicated that investigation of higher intensity tDCS is warranted (Nitsche et al. 2017) The only side effects that have been reported when proper guidelines are followed are temporary tingling, itching, headache, or skin redness under the electrodes in some subjects. For example, a 2008 review of the approximately 100 human tDCS studies up until that time on healthy adults and patients found that 64 of these studies reported no side effects, 24 studies reported a temporary itching or tingling under the electrodes in some subjects, and one study reported skin redness. Furthermore, these slight side effects were of equal occurrence in subjects that received placebo stimulation in 7 studies. In addition, only two subjects in these 100 studies reported a mild headache. Similar findings have recently been reported in research and review articles (Nitsche et al. 2008; Hummel et al. 2008).

Physiological studies have also assessed the safety of tDCS when applied within the aforementioned stimulation guidelines. For example, there was no neuronal damage as measured by serum neuron-specific enolase (Stagg & Nitsche, 2011) or MRI measures of edema using contrast enhanced and diffusion-weighted MRI measures following administration of tDCS (Nitsche et al. 2004). Furthermore, tDCS did not negatively alter measures of neuropsychological function and EEG activity (Iver et al. 2005). Accordingly, rat studies using tDCS models emulating tDCS applied to humans (Liebetanz et al. 2009) showed that the current density needed to induce tissue damage or lesions was about  $1429 \text{ mA/cm}^2$ , whereas the current densities used in human studies are between  $0.04$  and  $0.08 \text{ mA/cm}^2$  and in this proposal are  $0.029 \text{ mA/cm}^2$  and  $0.11 \text{ mA/cm}^2$ . Lastly, safety and tolerability results from two of our recent studies currently under review for publication provide evidence that 4 mA tDCS is safe and well-tolerated, with most sensations and sensation severities similar to sham and 2 mA tDCS. In conclusion, the tDCS stimulation parameters in this study are identical to the most common in the literature and have been proven to be exceptionally safe and well-tolerated.

The probability is very unlikely that harm may occur (see above). Based on the available literature a slight headache should be the worst possible negative effect and should be very rare. In this case, non-prescription medication should relieve the headache within 1-2 hours.

PwMS in general have a higher fall risk.

There are no emotional or psychological, financial, legal or social risks.

This was a case report: No statistical analysis.

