## Transcranial Direct Current Stimulation to Lower Neuropathic Pain in People With Multiple Sclerosis

Purpose

The purpose of this study is to investigate the effects of different intensities of transcranial direct current stimulation (tDCS) on neuropathic pain and fatigue in people with MS. We will conduct three different tDCS conditions (sham, 2 mA, and 4 mA) on 5 consecutive days each. We will evaluate pain and fatigue with specific questionnaires and measure fatigability with an isokinetic device.

Our research question is whether tDCS can lessen neuropathic pain and increase fatigue resistance in people with MS and if a higher intensity stimulation (4 mA) provides additional pain and fatigue improvements. We hypothesize less neuropathic pain and increased fatigue resistance after either of the tDCS sessions and that the 4 mA condition will better improve pain and fatigue compared with the 2 mA condition.

Significance and Background

People with Multiple Sclerosis (PwMS) are at an over five-fold increased risk of receiving treatment for neuropathic pain. This pain type appears to be the primary factor behind the overall increased risk of pain treatment for PwMS. However, the management of neuropathic pain syndromes is currently a challenging task because only 40% to 60% of patients experience a favorable outcome from pharmacological treatments. Several studies have shown that most of the currently available treatments, including antidepressants, opioids, and topical anesthetics, have limited long-term effectiveness and are often associated with moderate or even severe adverse effects. It is generally agreed that improved therapies are needed for addressing symptoms of MS such as neuropathic pain. Furthermore, to fight the opioid epidemic in the US, safer treatments are urgently needed.

tDCS has significantly advanced in the past 15 years as a treatment tool and has been successfully used by the PI. It has a theoretical advantage when compared with traditional neuropathic pain treatments because it directly affects central neural targets, thus having a potentially stronger effect on central sensitization. On the other hand, its effects may take longer to appear (i.e., only after 5–10 sessions, subjects may notice pain decrease). Because of its relatively low cost, ease of use, and safety profile, tDCS may be a suitable alternative treatment of pain in various disorders.

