tDCS treatment protocol: A tDCS device (Soterix) will deliver a small direct current through two sponge surface electrodes (5cm x 5cm, soaked with 15 mM NaCL). The positive electrode will be placed over the motor cortex representation of the more affected leg, and a second electrode will be placed on the forehead above the contralateral orbit. The three protocols blocks (sham, 2 mA, 4 mA) will be performed in randomized order.

tDCS Block: The participant will receive tDCS for 20 min at an intensity of 2 mA or 4 mA while seated comfortably and quietly in a room. The intensity will start at 0 mA and will be incrementally increased to 2mA or 4 mA over the initial 30 seconds. At the 19:30 minute time point, the current will gradually be reduced from 2 mA (or 4 mA) to 0 mA.

Sham block: Identical to the tDCS block, except the participants will only receive the initial 30 seconds of ramp-up, after which the current will be set to 0 for the remainder of the 20 minutes.

The remaining sessions of first block (i.e. Block 1, Sessions 2-5) will be as follows: In Sessions 2 and 4, the subjects get the tDCS or sham treatment, after which they will complete the fatigue and pain questionnaires (FSS and NPQ). Sessions 3 will be the same as Sessions 2 and 4, except that the isokinetic fatigue test will be performed at the beginning (i.e., before the tDCS or sham treatment). Session 5 will start with tDCS or sham treatment, then the isokinetic fatigue test, and finally the fatigue and pain questionnaires.

Blocks 2 and 3 will be completed in the same manner as Block 1, except that the subjects will not redo the PDDS, VAS, and BDI in Session 1 and the treatment will shift to either tDCS at 2 mA, tDCS at 4 mA, or sham, depending on how the blocks were randomized. Block 2 will be randomly assigned based on uncompleted stimulation blocks.

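### The safety conclusion calls all stimulation parameters the most common in the literature and proven safe, which the protocol's own text contradicts for 4 mA

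*Protocol*

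**What the plan says.** The study has two active intensities and a sham. Under tDCS treatment protocol, the active block is described so: "The participant will receive tDCS for 20 min at an intensity of 2 mA or 4 mA". The current passes through "two sponge surface electrodes (5cm x 5cm, soaked with 15 mM NaCL". The Purpose presents 4 mA as the departure from the lower level, asking "if a higher intensity stimulation (4 mA) provides additional pain and fatigue improvements".

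The tDCS safety text in Risks for subjects then makes these statements:

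- Safety is said to depend on how strong the current is, how large the electrode is and how long stimulation lasts. The text adds that "experts in tDCS research have indicated that investigation of higher intensity tDCS is warranted".
- On density it reads "whereas the current densities used in human studies are between" 0.04 and 0.08 mA/cm², "and in this proposal are" 0.029 and 0.11 mA/cm².
- On 4 mA in particular it says that "safety and tolerability results from two of our recent studies currently under review for publication provide evidence that 4 mA tDCS is safe", adding that most sensations and their severities resembled those under sham and 2 mA.
- It then concludes, for the study as a whole, that "the tDCS stimulation parameters in this study are identical to the most common in the literature and have been proven to be exceptionally safe".

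The next paragraph says that, on the available literature, a mild headache is the worst effect to expect. It does not separate the intensities either.

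**The concern.** The conclusion makes two claims about every stimulation parameter in the study: that it matches the commonest practice in the literature, and that its safety is proven. If either claim fails at one active level, the protocol asserts a safety property that its design does not have at that level.

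This matters because of where the sentence stands. It closes the risk assessment that a review board reads, and Enrollment and Consent undertakes that subjects will hear of every potential risk before signing. A reader who relies on the closing sentence would take 4 mA to have the same standing as the commonest published settings. The sentences just before it say otherwise.

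**Working it through.** **Inputs.** Currents of 2 and 4 mA and an electrode of 5 cm × 5 cm = 25 cm² (tDCS treatment protocol). Human-study range of 0.04 to 0.08 mA/cm² and this study's densities of 0.029 and 0.11 mA/cm² (Risks for subjects).

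**Formula.** Density = current / electrode area.

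**Step 1: try to reproduce the printed densities.**

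| Current | Area | Computed | Printed |
|---|---|---|---|
| 2 mA | 25 cm² | 2/25 = 0.08 mA/cm² | 0.029 mA/cm² |
| 4 mA | 25 cm² | 4/25 = 0.16 mA/cm² | 0.11 mA/cm² |

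Neither printed value is reproduced. No single electrode area gives both: the printed pair has a ratio of 0.11/0.029 = 3.8, while the currents have a ratio of 4/2 = 2. Worked backwards, 0.11 at 4 mA implies 4/0.11 = 36.4 cm², and 0.029 at 2 mA implies 2/0.029 = 69.0 cm². If one assumes a 35 cm² electrode, which the protocol does not mention, then 4/35 = 0.114 and 1/35 = 0.0286. The printed pair would then fit 4 mA and 1 mA, and 1 mA is not a level in this study.

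**Step 2: compare 4 mA with the quoted range.**

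- Printed value: 0.11/0.08 = 1.375 times the upper limit.
- Value from the stated electrode: 0.16/0.08 = 2.0 times the upper limit.

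The contradiction does not depend on which figure is right, because both lie above the range.

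**Step 3: set the wording side by side, at 4 mA.**

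| Conclusion | Elsewhere in the protocol |
|---|---|
| Same as the commonest in the literature | Density above the range quoted for human studies |
| Same as the commonest in the literature | Higher intensity is something experts say should be investigated, and the Purpose makes 4 mA the higher level under test |
| Proven safe | The only evidence specific to 4 mA is two of the team's own studies, still under review |
| Proven safe, no exception | Most, not all, sensations and severities resembled sham and 2 mA |

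The section's own premise, that safety depends on current strength, also blocks a simple carry-over. General tDCS evidence cannot be extended to 4 mA unless the text says what intensities that evidence covered, and it does not.

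**The case against.** The strongest reply is that the protocol hides nothing. The sentence immediately before the conclusion reports the 4 mA studies, says that they are under review and limits the similarity to most sensations. On this view the closing sentence is loose wording, and the only numerical conflict is the density error, which needs correcting anyway.

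The disclosure is real, so the fault is not a complete lack of evidence for 4 mA. But the next sentence overrides the disclosure with a conclusion that admits no exception. Correcting the densities from the stated electrode does not repair it either, since 0.16 lies further above the range than 0.11. The density error and this point share figures and should be corrected together.

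Several stronger readings are tempting, and the documents do not support them:

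- *That 4 mA is unsafe.* A density above a quoted range, together with unpublished support, does not show harm.
- *That participants are told 4 mA is the commonest level and proven safe.* The consent text is not shown, so its wording is unknown.
- *That this sentence is the protocol's reason for using 4 mA.* The stated reason is possible added benefit, and the safety support offered is the separate sentence on the two studies.
- *That the published evidence was obtained at 2 mA, so the conclusion stands for that level.* The intensities in the roughly 100 reviewed studies and in the physiological studies are not given. The printed 0.029 lies below the quoted range, and the recomputed 0.08 is at its upper edge.
- *That the 2008 review is confined to the guidelines mentioned earlier in the text.* That phrase introduces the physiological studies. The review illustrates a different statement, about side effects when proper guidelines are followed.
- *That planned session counts measure the problem.* They describe intended exposure, not the effect of the wording. The document also ends by calling the work a case report, so actual exposure may have been smaller.

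**Conclusion.** The point holds for 4 mA. The statement that all the study's parameters match the commonest in the literature and are proven safe is wrong as written at one of the two active intensities. On the protocol's own figures the 4 mA density is between 1.375 and 2.0 times the upper limit quoted for human studies. The specific support is two studies not yet published.

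This rests on reading the conclusion as covering both active levels, which its wording requires. It also rests on taking the quoted range of 0.04 to 0.08 mA/cm² as the protocol's own account of human practice. It needs no outside source and does not depend on which density is correct. It is no judgement on the safety of 4 mA or on which intensity should be used. Because the sentence closes the risk assessment and the correction is cheap, it should be made.

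**What to change.** In Risks for subjects:

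1. Remove, as applied to 4 mA, the claim that the parameters match the commonest in the literature and are proven safe.
2. State instead that the 4 mA density lies above the range quoted for human studies, and that the support specific to 4 mA is two of the team's own studies, not yet published.
3. Qualify the sentence on headache as the worst expected effect in the same way.
4. Reconcile the conclusion with the printed densities, the 5 cm × 5 cm electrode and the statement that higher intensity should be investigated.
5. Check that the risk text in the consent form, which is not shown, agrees with the revised section.

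The cost is rewording in one section and, if the check requires it, matching consent text. The downside is a less favourable safety statement for 4 mA. The choice of intensities remains with the investigator and the review board.

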**Inclusion Criteria:** medically diagnosed with Multiple Sclerosis, 18-70 yrs. of age, moderate disability (Patient Determined Disease Steps (PDDS) core 2-6), self-reported differences in function between legs, able to walk for 6 min, and presenting with chronic, drug-resistant, neuropathic pain. Chronic neuropathic pain will be defined as a constant or intermittent sensory symptom with unpleasant feelings or pain, lasting more than 1 month and having a stereotyped neurological distribution and superficial localization. To differentiate neuropathic from spasticity-associated pain, patients need to score greater than 0 on the Neuropathic Pain Questionnaire (NPQ) to qualify for the study. A minimum score of 40 (0 = no pain, 100 = worst possible pain) on the visual analog scale (VAS) for pain perception at baseline will be required to be enrolled in the study. All analgesic medications will be discontinued at least 24 hours before entering the study and not be used until study participation is completed.

**Exclusion Criteria:** relapse within last 60 days, high risk for cardiovascular disease (ACSM risk classification), changes in disease modifying medications within last 45 days, concurrent neurological/neuromuscular disease, hospitalization within last 90 days, diagnosed depression, and inability to understand/sign informed consent.

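### The risk section leaves out the trial-imposed stop of all analgesics, and the headache remedy it relies on is not reconciled with that stop

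*Protocol*

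**What the plan says.** The protocol's Inclusion Criteria admit people "presenting with chronic, drug-resistant, neuropathic pain" whose baseline pain on the visual analog scale is at least 40, where 100 is the worst possible. The same paragraph ends with the medication rule: "All analgesic medications will be discontinued at least 24 hours before entering the study and not be used until study participation is completed". It gives no exception and does not define which drugs count as analgesics.

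The section Risks for subjects covers the following:

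- On physical well-being: "Potential risk include muscle cramps/spasms during strength testing".
- On stimulation, after a review of the literature: "a slight headache should be the worst possible negative effect and should be very rare". It then adds: "In this case, non-prescription medication should relieve the headache within 1-2 hours".
- A remark that people with MS fall more often.
- A closing statement: "There are no emotional or psychological, financial, legal or social risks".

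The analgesic stop does not appear there. Enrollment and Consent promises that "the subject will be informed of all potential risks before signing the consent document" and allows withdrawal at any time for any reason.

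**The concern.** The stop is something the trial does to participants, and they are selected for having substantial pain. More pain is its most direct possible consequence, and that is a physical risk. Distress may follow. Symptoms from discontinuing a drug are also possible for anyone whose drug can cause them. None of this is in the section meant to set out the risks, and the closing sentence rules out emotional and psychological risk altogether.

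The headache text raises a second problem. Site staff who read the Inclusion Criteria would tell a participant with a headache to take nothing. Staff who read the risk section would expect an over-the-counter remedy. At stake are the accuracy of the protocol's own risk assessment, which should support the promise to disclose all risks, and consistent handling of the one side effect for which the protocol mentions a treatment.

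**Working it through.** **1. How long the stop lasts.** The protocol states no figure, so there is none to reproduce. The inputs are:

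- three blocks, at least one week apart (Methods);
- five consecutive days per block (Purpose; Methods);
- a stop beginning at least 24 hours before entry and lasting to the end of participation (Inclusion Criteria).

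With b blocks and g free days between blocks, the minimum number of days is D = 5b + (b − 1)g + 1, where the last term is the day before entry.

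| Reading | b | g | D |
|---|---|---|---|
| Seven days from last session to next first session | 3 | 6 | 15 + 12 + 1 = 28 |
| Seven full free days | 3 | 7 | 15 + 14 + 1 = 30 |
| Monday–Friday blocks with a full week off | 3 | 9 | 15 + 18 + 1 = 34 |
| Week counted from start to start | 3 | 2 | 15 + 4 + 1 = 20 |
| Two blocks only, six free days | 2 | 6 | 10 + 6 + 1 = 17 |
| Two blocks, week counted start to start | 2 | 2 | 10 + 2 + 1 = 13 |

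The natural reading is three blocks with a week separating the end of one from the start of the next, which gives at least 28 days. The two-block rows arise only because Enrollment and Consent mentions 10 visits, whereas three blocks need 3 × 5 = 15. Every row is a minimum, since both the separation and the 24 hours are set as lower limits and no maximum per participant is given.

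**2. Procedures against listed risks.** Strength testing is matched by cramps and spasms. Stimulation is matched by skin sensations and headache. The disease itself is matched by falls. The analgesic stop has no matching entry.

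**3. Headache remedy against the ban.** The Inclusion Criteria bar all analgesics until the end of participation. The risk section expects non-prescription medication to relieve a headache. It names no drug, but such a remedy would ordinarily be an analgesic. Neither place refers to the other or states an exemption.

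**4. Scope of the ban.** Significance and Background lists antidepressants and opioids among the available treatments for this pain. The Inclusion Criteria do not say whether a prescribed antidepressant or opioid counts as an analgesic. If it does, the rule as worded permits stopping it only 24 hours before entry. Excluding diagnosed depression does not settle this, because the protocol itself presents antidepressants as a pain treatment. What participants actually take is not stated; anything from 0 to 20 of the 20 could be on such drugs.

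**The case against.** An analgesic-free period is a defensible choice in a pain trial, and several features soften its effect. The pain must be drug-resistant, and the background section describes most current treatments as having limited long-term effect and frequent adverse effects. Stopping them may therefore cost some participants little. Diagnosed depression is excluded, the pain questionnaire is completed at every session, and withdrawal is free. These points stand as mitigation. They do not justify the omission, because a poor response is not the same as no benefit, and no action is attached to the questionnaire scores.

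Four stronger readings are tempting and are not supported:

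- *A participant with a headache has no permitted relief short of withdrawal.* The specific headache sentence can be read as qualifying the general ban, and non-drug relief is barred nowhere. The text is in conflict or unclear; it does not plainly forbid relief.
- *Participants are not told about the stop.* The consent pages were removed from the file and may disclose it, and the protocol commits to telling subjects about all potential risks.
- *The protocol claims that nothing worse than a headache can happen.* That sentence follows the stimulation literature and concerns stimulation only.
- *Participants will suffer withdrawal symptoms.* This depends on drug use that the protocol does not report.

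It is also fair to say that the link from the stop to psychological risk is inferred. The firmer part of the point is the missing entry for the stop and the extra pain it may cause.

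**Conclusion.** The point holds as a gap and an inconsistency within the protocol's own risk section and medication rule. A trial-imposed stop of all analgesics, in people with pain of at least 40 out of 100, is not listed as a risk. The categorical denial of emotional and psychological risk cannot be sustained beside it. The headache remedy and the ban conflict or, at best, leave staff unsure.

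The stop lasts at least 28 days on the natural three-block reading. This is derived and not stated. It assumes that the week runs from the last session of one block to the first of the next, and that the 24 hours before entry count as one day. The less natural readings shorten it to between 13 and 20 days without changing the conclusion. The size of any harm cannot be estimated, because neither drug use nor the benefit lost on stopping is given.

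This should be corrected. The omission is certain from the text, while the harm to an individual is not established. The protocol's closing remark that this was a case report has no clear meaning here. If participation is already over, the change helps only further participants.

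**What to change.** 1. In Risks for subjects, list analgesic discontinuation as a study risk: more pain, possible distress, and discontinuation symptoms where the stopped drug can cause them. Remove emotional and psychological risk from the closing denial; the financial, legal and social part can stay. Check that the consent text matches.
2. In the Inclusion Criteria, exempt one named non-prescription drug for headache, with dose and time recorded. State whether prescribed antidepressants and opioids fall under the ban, so that they are not stopped abruptly on 24 hours' notice.

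The cost is one amendment, a consent check and a short log of rescue use, with no extra visits. The downsides are a less favourable risk statement and occasional recorded rescue use that may slightly affect pain scores.

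Rescue for worsening pain and a referral step to a clinician are optional. They are design preferences, and wider rescue would trade against the pain outcome.
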